11.9 Analysis Methods

Analysis (for 6-month and 12-month follow-up): Random-effects regression models. Covariates at individual level: participant age group, sex, IMD 2015 quintile, IDACI 2015 quintile, Borough, and the baseline questionnaire outcome score. Covariates at cluster level: mean IMD 2015, mean IDACI 2015, number of children under 16 years, rate of paediatric OP referrals 2015-16, and the mean baseline questionnaire outcome score.

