5. SAMPLE SIZE, RECRUITMENT, RANDOMISATION, AND BLINDING

5.1 Sample size and power

Population Evaluation

Pseudo-anonymised data from all children (<16 years) within participating practices will be used to analyse the impact of the CYPHP Evelina London model on health service use.

11 clusters in each arm, and an average of 3800 CYP per cluster, provides over 87% power to detect a reduction of 20% in the rate of non-elective admissions, assuming a coefficient of variation of 0.142, as explained below.

The number of CYP per cluster is estimated conservatively based on the 89382 CYP (age 0-15) registered in 2015 in the GP practices in the 23 randomised clusters. For each financial year 2013-14 – 2015-16, the baseline rate of non-elective admissions and the coefficient of variation was estimated using counts of non-elective admissions per cluster from financial years 2013-14 – 2015-16, and counts of CYP enrolled per cluster during 2013-2015. The coefficient of variation used in the sample size calculation was the mean of these three estimates. The rate of non-elective admissions was the total rate estimated by combining data from the three financial years.

Tracer Condition Evaluation

With 11 clusters in each study arm, the study team will need to recruit a minimum of 1006 CYP with a long-term tracer condition (asthma, constipation or eczema) per arm (total 2012). This number of participants will give the study 90% power to detect a mean minimum clinically important difference (MCID) of 4.5 points (standard deviation 16.5) in the primary child-health outcome tool (parental reported PEDSQL (Varni et al, 1999),² as used previously with children with chronic health conditions such as asthma (Varni et al, 2004).⁸ Intraclass coefficient (ICC) is assumed to be 0.02 based on study of quality of life in children and young people with a related condition, hay fever (Hammersley et al, 2010). Inter-cluster variation is assumed to be (0.03) based on the harmonic mean and variance of cluster size derived from GP registrations. This number also accounts for a 30% loss to follow up.

In total there are **23 clusters**, 12 in one arm and 11 in the other. As such the outlined sample size underestimates the total power as we have assumed 11 clusters in each arm.

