- provide informed consent for the evaluation team to 1) access their child's clinical details including a baseline clinical screening questionnaire which is completed on entry into the clinical service, and 2) have access to, and link, the child's GP and hospital data to assess the impact of CYPHP on both primary and secondary health service use. The baseline clinical screening questionnaire, completed for clinical services, includes the Strengths and Difficulties Questionnaire, and a condition-specific questionnaire: Asthma Control Test, GSTT Symptom Severity Measure (for constipation), or Patient Oriented Eczema Measure.
- complete an evaluation questionnaire at baseline (including health related quality of life measured by PEDSQL and CHU9D, and parental wellbeing measured by the Warwick-Edinburgh Mental Wellbeing Scale), and complete the clinical screening questionnaire and evaluation questionnaire at 6-month, and annual follow-up.
- give informed consent to be contacted to potentially participate in qualitative studies evaluating the service

Patient information sheets will make it clear that parents can consent or refuse consent to any of these components. Participants will be free to withdraw consent without prejudice at any time.

A parent/carer alone or with their child may be involved in the recruitment process. If the CYP is under 12 years of age the parent/carer will be asked to provide, on behalf of the child, informed consent, if they are happy to take part in the evaluation. If the CYP is between 12 and 16 years of age, the parent will be asked to provide informed consent and if the CYP is available at the time when parental consent is requested, the CYP will be asked to provide assent if they wish to participate.

TRACER CONDITION RECRUITMENT TIMELINE

Recruitment began in April 2018. The first participant was consented 22MAY2018, following their Health Check 24APR2018. Recruitment is planned to complete in December 2020.

POPULATION EVALUATION DATA

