18. PROTOCOL DEVIATIONS

18.1 Protocol changes related to COVID-19 Pandemic

Due to the COVID-19 pandemic, there was a trial pause, 12MAR2020 – 04JUL2020. Any individual consented data collection that occurred during the pause was repeated after the pause. Also, for participants enrolled in the study before the pause, the time points for follow-up data collection after the pause were delayed by the length of this pause, to ensure all study participants had the opportunity to be exposed to the intervention (or control) for the relevant time periods (6 months and 12 months) before follow-up data collection. Data collected during the pause may be used for secondary analyses. See appendix for diagram.

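### The pooled PedsQL and WEMWBS models (SAP 11.9) adjust for neither tracer condition nor recruitment period, though recruitment pools three conditions and crosses the pandemic pause

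*SAP*

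**What the plan says.** SAP 11.9 sets one covariate list for the random-effects models at both follow-up times. At the individual level it reads "Covariates at individual level: participant age group, sex, IMD 2015 quintile, IDACI 2015 quintile, Borough, and the baseline questionnaire outcome score". At the cluster level it reads "Covariates at cluster level: mean IMD 2015, mean IDACI 2015, number of children under 16 years, rate of paediatric OP referrals 2015-16", together with the cluster mean of the baseline score. No other section adds condition or calendar period to these models.

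The comparison is pooled over conditions: the sample size in 5.1 counts "CYP with a long-term tracer condition (asthma, constipation or eczema) per arm". Sections 8.4 and 8.5 name the three conditions as subpopulations, but nothing stratifies or adjusts the pooled analysis by them.

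On timing, 5.2 dates the first consent to 22 May 2018 and states that "Recruitment is planned to complete in December 2020". Section 18.1 records that "Due to the COVID-19 pandemic, there was a trial pause", from 12 March to 4 July 2020. Individual data collected in that interval were collected again afterwards, and later follow-ups were moved back by the same length of time. Section 6.4 allows each follow-up to run up to 4 months late. The primary PedsQL endpoint is the total score at 6 months (11.1).

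**The concern.** Randomisation of 23 clusters was stratified by borough and restricted on deprivation, child population and outpatient referrals (5.3), not on condition mix or recruitment pace. Consent comes after allocation (5.2), and participants and services are not blinded (5.4). Who consents, with which condition and when, is therefore not balanced by design.

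Both factors plausibly predict quality of life and parental wellbeing, and both are known at baseline. Children recruited at different dates fall into three groups for the 6-month endpoint: both forms before the pause, baseline before and follow-up after, or both after. A change in level between the two forms enters the follow-up score and not the baseline score. If one arm has more children in the middle group, that change enters the arm estimate. If only clusters differ, it adds between-cluster noise.

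The variables named for the baseline table in 14.1 include neither condition nor recruitment period, so an imbalance might also go unseen.

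**Working it through.** **The plan's own figure.** Inputs from 5.1: difference 4.5, SD 16.5, power 90%, 11 clusters per arm, 30% loss, and "Intraclass coefficient (ICC) is assumed to be 0.02". Two-sided alpha of 0.05 is assumed, since 5.1 does not state it.
- Individually randomised size: 2 × (1.960 + 1.282)² × 16.5² / 4.5² ≈ 282.5, i.e. 283 per arm.
- With a fixed number of clusters, using 11 − 1 = 10 in the formula: m = 282.5 × 0.98 / (10 − 282.5 × 0.02) ≈ 63.7 per cluster.
- 11 × 63.7 ≈ 700 analysed, and 700 / 0.70 gives 1001 recruited per arm, against 1006 stated.
- Check: 1006 × 0.70 = 704 analysed, 64 per cluster, design effect 1 + 63 × 0.02 = 2.26, power 89.9% (t, 20 df).

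The figure reproduces and does not depend on the covariates discussed here.

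**Timing groups at 6 months.** Recruitment is assumed uniform from 22 May 2018 to 31 December 2020, outside the 115-day pause, giving 840 days. Adding 6 months, or 6 + 4 = 10 months, to the baseline date gives:
- Baseline before 12 May 2019: 355 days, 42%. Follow-up precedes the pause even at the end of the window.
- 12 May to 11 September 2019: 123 days, 15%. Due before the pause, but may fall later within the window.
- 12 September 2019 to 11 March 2020: 182 days, 22%. Pre-pause baseline with post-pause follow-up.
- 5 July 2020 onward: 180 days, 21%. Both forms after the pause.

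Nominally, 355 + 123 = 478 days (57%) have both forms before the pause and 22% straddle it. If the whole window is used, (123 + 182) / 840 = 36% could straddle it.

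**Bias from timing.** Bias = shift between baseline and follow-up × arm difference in the share affected. The documents give neither quantity, so both are assumed.
- 3 points × 0.10 = 0.3 points; 0.3 / 4.5 = 7% of the MCID.
- 5 points × 0.10 = 0.5 points; 0.5 / 4.5 = 11%.
- No arm difference: 0.

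On the z-score scale of 11.1, taking SD 16.5, 0.3-0.5 points is about 0.02-0.03 SD.

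**Bias from condition mix.** A stable gap between conditions is present at baseline too. With an assumed follow-up-on-baseline slope of 0.5-0.7, the remainder is 1 − slope. A 5-point gap with a 10-percentage-point imbalance falls from 0.5 to about 0.15-0.25 points.

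**Type I error.** This was a null simulation with 23 clusters, 61 analysed per cluster, ICC 0.02, baseline correlation 0.6, a 5-point gap and 3000 replicates. Adjustment was idealised, with the covariate effect removed exactly.
- No systematic imbalance: about 0.05 without adjustment.
- 10-percentage-point systematic imbalance: about 0.07-0.08 without adjustment, about 0.05 with it.

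**Precision.** Planned between-cluster variance is 0.02 × 16.5² = 5.4. If the affected share varies between clusters with SD 0.15-0.25 (assumed) and the shift is 3-5 points, the added variance is (3 × 0.15)² = 0.20 to (5 × 0.25)² = 1.56. The planned variance of a cluster mean is 5.4 + 0.98 × 16.5² / 64 = 9.6, so the standard error rises by about 1-8%.

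**The case against.** The strongest reply is that bias needs an actual difference between arms, and the SAP documents none. One recruitment process serves both arms (5.2), Health Checks run in both (4.1), recruiting researchers are to be blind (5.4), and the pause was trial-wide. Chance imbalance is variance rather than bias, and the cluster random effect largely carries it. This stands, with one reservation: 11.10 lets the analysis fall back to standard regression when little clustering is seen, and no random effect then remains.

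The child's own baseline score and the cluster mean are already in the model and absorb much of a stable gap between conditions. This stands, and it makes the condition part the weaker one. It also partly covers children with both forms after the pause. It does not cover those who straddle it.

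Section 18.1 repeats pause data and moves later follow-ups. That protects exposure time and keeps responses given during the pause out of the main analysis, but it does not model a before/after change in level.

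The present list is coherent: the stratification and restriction factors plus age, sex and baseline. Nothing in it contradicts another section. It is also true that measured covariates cannot repair unmeasured selection into consent.

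A reader might infer that differences in mix or timing are in fact being reported as treatment effect, or that a bias of 1 point or more is likely. The documents do not support that. A 20-percentage-point imbalance in a group of about 22% would mean roughly 12% against 32%. With a cluster SD of 0.15-0.25, the standard error of the arm difference in share is SD × √(1/11 + 1/12) = 0.06-0.10, so 20 points lies 2-3 standard errors out.

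**Conclusion.** The omission is plain in 11.9 and is not made good elsewhere. It leaves both primary questionnaire outcomes open to bias or lost precision if arms or clusters differ in recruitment timing or condition mix. It does not show that either has happened.

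The timing part carries the point, because own-baseline adjustment cannot remove a change arising after baseline. About 22% of children are nominally exposed to this at 6 months, and up to 36% if the follow-up window is fully used, assuming uniform recruitment. The condition part is secondary.

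The plausible size is modest: 0.3-0.5 points, 7-11% of the MCID, under an assumed 3-5 point shift and a 10-percentage-point imbalance, and zero if the arms are balanced. The case for change rests on low cost: both variables are available at baseline and can be specified in advance.

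**What to change.** Add to the individual-level covariates in 11.9:
- (a) indicators for asthma, eczema and constipation;
- (b) a recruitment-period factor defined only by baseline date, with cuts that allow for the 4-month window. For the 6-month analysis, for example: before 12 May 2019; 12 May to 11 September 2019; 12 September 2019 to 11 March 2020; 12 March 2020 onward. The last category gives a place to anyone consented during the pause.

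For 12 months, counting back 16 and 12 months from 12 March 2020 gives cuts at 12 November 2018 and 12 March 2019, then 12 March 2020.

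Use baseline date rather than actual follow-up date, so that nothing arising after entry is conditioned on. The second category will still mix follow-ups before and after the pause; that is the price of this choice. In 14.1, tabulate condition and recruitment period by arm.

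The cost is three degrees of freedom for period and two or three for condition, out of about 2 × 704 = 1,408 analysed children. The recruitment target does not change.

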11.10 Intracluster correlation and regression models

Above we have described planned random-effects regression models, to account for clustering by randomised GP cluster. However, when we observe minimal correlation within clusters, these models are not appropriate, and we will report results from standard regression models, controlling for both the individual-level and cluster-level covariates described above.

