5.3 Randomisation

As part of the implementation of the CYPHP Evelina London model within Lambeth and Southwark, GP practices are grouped into virtual clusters. Clustering is a pragmatic clinical delivery decision, because it allows sharing of resources and holding specialist in-reach clinics without added expense to the practices. Where possible clusters were created aligned to GP Federation "neighbourhoods" or other groupings.

Of the 100 GP practices within Lambeth and Southwark, 25 took part in pilot testing of some components of the CYPHP Evelina London model of care to refine the model and test feasibility. As such these 25 practices are not randomised. All other practices are eligible to take part in the trial evaluation.

Randomisation is at the level of the primary care practice cluster. 23 clusters were randomised, by an external statistician.

Randomisation was stratified by borough, and restricted with the following restriction factors:

- Baseline Index of Multiple Deprivation (IMD) / Income Deprivation affecting children Index (IDACI) score per cluster
- CYP population <16 per GP cluster
- Paediatric OP referrals 2015-2016

These restrictions factors are believed to affect health related quality of life and patterns of health service use. Restricted randomisation on these factors helps to ensure that clusters are comparable with regards to (i) number of patients within each cluster, (ii) the socio-demographic profile of their patient population (iii) the referral patterns within clusters.

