11. PARTICIPANT-REPORTED OUTCOME DEFINITIONS AND ANALYSIS METHODS

11.1 Tracer condition analysis – Primary child outcome – PedsQL

The Pediatric Quality of Life Inventory (PedsQL) is a brief measure of health-related quality of life in children and young people. This will be completed at baseline and each follow up. In all instances, the outcome for analysis will be parent-reported and child-related. However, where appropriate, child-reported outcomes will also be collected and reported.

Age versions: 0-12 months, 13-24 months, 2-4 years, 5-7 years, 8-12 years, 13-18 years

For 0-12 months and 13-24 months:

Subscales: Physical Functioning, Physical Symptoms, Emotional Functioning, Social Functioning, Cognitive Functioning

Summary scores: Physical health summary score (mean of physical functioning and physical symptoms), Psychosocial Health (mean of emotional, social, and cognitive scales), Total Score (mean of all scales)

For age 2+:

Subscales: Physical functioning, Emotional functioning, Social functioning, School functioning

Summary scores: Physical health summary score, Psychosocial Health (mean of emotional, social, and school scales), Total Score (mean of all scales)

Mismatch of questionnaire version and participant age: Treat as missing any questionnaires for ages 8+ completed by children age 0-4 at baseline.

Total score: Sum of items divided by the number of items answered for all scales.

- Items: There are 21-45 items in the PedsQL, depending on age of CYP; each item assigned value of 0, 25, 50, 75, 100.
- Missing data: use the mean value for items within the subscale. If more than 50% missing in a subscale, exclude the participant's data.

To combine data across ages:

- Check distribution of scores; transform if needed.
- Convert scores to z-scores (number of SDs above/below the trial mean).
- Analyse follow-up z-score, adjusted for baseline z-score for individuals.

Primary Outcome: Total Score at 6-month follow-up

Secondary outcomes from PedsQL: Physical Health score, Psychosocial Health score, same analysis method.

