11.8 A School & Work Absence questionnaire

- How many days of school has your child missed due to ill health or attending health-related appointments in the past three months?
 - Number of days
 - Other responses
 - My child is too young to attend school
 - My child is school age but does not attend school for health reasons
 - My child is school age but does not attend school for other reasons
 - I can't answer this question
- How many days of work have you missed in the past three months due to your child's illness or healthcare appointments?
 - Number of days
 - Other responses
 - I am not working because of my child's health needs
 - I am not working for other reasons
 - I can't answer this question

We will report the number of missing days, and also treat the outcome as binary (any absence or no absence). The binary outcomes will be analysed using logistic regression and with chi-squared tests.

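### Section 11.10 drops the GP-cluster random effect when observed correlation is 'minimal', a term it never defines; depending on the cut-off, overall type I error runs from nominal to about 11%

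*SAP*

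**What the plan says.** SAP section 5.3: "Randomisation is at the level of the primary care practice cluster". Section 5.1 gives 23 clusters, 12 in one arm and 11 in the other, and for the tracer-condition sample size "Intraclass coefficient (ICC) is assumed to be 0.02".

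Section 11.9, for the questionnaire outcomes: "Analysis (for 6-month and 12-month follow-up): Random-effects regression models". It lists individual-level covariates and then "Covariates at cluster level: mean IMD 2015, mean IDACI 2015, number of children under 16 years, rate of paediatric OP referrals 2015-16", together with the cluster mean of the baseline score. These outcomes include the primary child outcome (section 11.1: "Primary Outcome: Total Score at 6-month follow-up") and the primary parental outcome, WEMWBS (section 11.3).

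Section 11.10 states that the random effects are there to account for the randomised GP clusters, but that "when we observe minimal correlation within clusters, these models are not appropriate, and we will report results from standard regression models", keeping the individual-level and cluster-level covariates. It gives no ICC cut-off, test or model-fit criterion, and no robust or cluster-level standard error in place of the random effect.

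Section 11.8, on school and work absence: "The binary outcomes will be analysed using logistic regression and with chi-squared tests". No cluster adjustment is mentioned for the chi-squared tests.

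**The concern.** In a cluster-randomised trial the standard error of the arm comparison must carry between-cluster variation. Standard regression leaves it out. Cluster-level covariates may lower the residual ICC, but they supply neither a cluster-level error term nor cluster-level degrees of freedom.

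A small observed ICC is no reason to call the random-effects model inappropriate. If the estimated variance is zero, the model simply reduces to standard regression. If the estimate is small but positive, the model is still valid and its standard error still differs from the naive one. With 23 clusters the estimate is imprecise, so a low value is weak evidence that the true ICC is zero.

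At stake is whether the two primary participant-reported results keep their nominal error rate. As 'minimal' is left open, the SAP does not fix which analysis will be reported.

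**Working it through.** **The plan's own figure.** Inputs from section 5.1: difference 4.5, SD 16.5, power 90%, ICC 0.02, 11 clusters per arm, 30% loss. A two-sided 5% level is assumed, as section 5.1 states none.

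- Without clustering: n = 2 × (16.5/4.5)² × (1.96 + 1.2816)² = 282.5, so 283 per arm.
- With clustering and one extra cluster per arm: k = 1 + n[1 + (m − 1)ICC]/m. Setting k = 11 gives m = 63.7, rounded to 64 per cluster, or 704 analysed per arm.
- With loss: 704/0.70 = 1005.7, so 1006 per arm. This is the SAP's figure.

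The trial is therefore sized on the basis that an ICC of 0.02 matters: 704 analysed per arm against 283.

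**Analysed children per cluster.** 2012 × 0.7 / 23 = 61.

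**Standard regression when the true ICC is not zero.** Design effect DE = 1 + (m − 1)ICC; type I error = 2 × P(Z > 1.96/√DE). For m = 61:

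| True ICC | DE | Type I error |
|---|---|---|
| 0.005 | 1.30 | 8.6% |
| 0.01 | 1.60 | 12.1% |
| 0.02 | 2.20 | 18.6% |

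**The whole rule.** The SAP switches only on a low estimate, so the relevant quantity is the error of the rule as a whole. It was simulated under the null: 11 v 12 equal clusters, m = 61, no covariates, 300,000 trials per ICC. Standard regression is used when the estimated ICC is at or below the cut-off, and a cluster-level t test on 21 df otherwise.

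| Assumed meaning of 'minimal' | ICC 0.005 | ICC 0.01 | ICC 0.02 |
|---|---|---|---|
| Estimate ≤ 0 | 4.6% | 4.9% | 5.1% |
| Estimate ≤ 0.005 | 5.6% | 5.7% | 5.4% |
| Estimate ≤ 0.01 | 7.0% | 7.5% | 6.5% |
| Estimate ≤ 0.02 | 8.3% | 10.9% | 11.1% |

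At a cut-off of 0.01 the switch fires in about 79%, 54% and 18% of trials at these three ICCs, so it would often fire when clustering is real. Keeping the cluster-level test throughout gives about 5% at every ICC.

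**Sensitivity.** At a residual ICC of 0.0025 the whole rule gives 4.3-6.8% over the four cut-offs; at zero there is no inflation. With 30 per cluster, a cut-off of 0.01 gives 5.2%, 5.6% and 5.7%, and a cut-off of 0.02 gives 6.1%, 7.0% and 7.6%.

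**Chi-squared tests in 11.8.** The same formula applies. The SAP gives no ICC for absence, and responses such as "My child is too young to attend school" reduce the number analysed, so both are assumed. At ICC 0.005, 0.01 and 0.02: 6.7%, 8.4% and 11.9% with 30 per cluster; 8.6%, 12.1% and 18.6% with 61.

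**Power if the term is always kept.** SE = 16.5 × √[(2.2/61) × (1/11 + 1/12)] = 1.308; 4.5/1.308 = 3.44. The noncentral t gives 90.6% on 23 − 2 = 21 df, and 89.5% on 21 − 6 = 15 df (five cluster-level covariates plus Borough).

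**The case against.** The best defence is that 'minimal' means a zero variance estimate. The random-effects fit then equals standard regression, 'not appropriate' is loose wording for 'redundant', and the overall error is not inflated. This stands for that reading, but the SAP does not state it.

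The largest figures need an estimate as high as 0.02 to count as minimal, which sits badly with a sample size built on that same ICC. This also stands: the 8.3-11.1% row is an upper end, not the likely case. If the kept model used a normal reference, its own error would be 5.4%, 5.9% and 6.3%, and a switch at 0.01 would raise it to 7.2%, 7.9% and 7.3%; the switch then adds only 1.0 to 2.0 points.

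A reader might infer that the primary results would be tested at 8.6%, 12% or 19% and that the switch causes all of it. The documents do not support that. Those are the errors of standard regression at a given true ICC. Selecting trials with a low ICC estimate raises the error of a cluster-level test too: where the estimate is zero or negative, the cluster-level t test errs in 10.3%, 13.3% and 19.6%, against 8.6%, 12.0% and 19.2% for standard regression. Nor is there ground to suggest steering towards a result: the trigger is the correlation and not the arm difference, and section 5.4 keeps the statistician blind to allocation. It is also unclear whether 11.10 reaches the Poisson models of section 10.9, so the point is confined to section 11.

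**Conclusion.** The point holds. Section 11.10 gives a wrong reason for dropping the cluster term and leaves the trigger undefined for analyses that include two primary outcomes. The excess in overall type I error runs from nil (zero variance estimate) through at most about 2.5 points (cut-off 0.01) to about 6 points (cut-off 0.02). This rests on a two-sided 5% test, equal clusters of 61, no covariates and a true residual ICC of 0.005 to 0.02. It is smaller if covariates lower the residual ICC or fewer children are analysed. The chi-squared tests in 11.8 are a separate and lesser fault: they concern secondary outcomes, and their 7-19% rests on an assumed ICC and assumed numbers. The sample size itself is not in question.

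**What to change.** In 11.10, delete the switch. Keep the GP-cluster random effect in every participant-reported arm comparison whatever ICC is observed, use a t reference on cluster-level degrees of freedom (21, or about 15 with the cluster-level covariates and Borough), and report the ICC. State in advance what is done if the variance estimate is zero or the model fails, for example a cluster-level analysis. Defining 'minimal' in advance as a zero variance estimate is an acceptable alternative, since it also removes the overall inflation.

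In 11.8, drop the chi-squared tests or replace them with a cluster-level comparison of proportions, and state that the logistic model carries the random effect of 11.9.

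The cost is SAP wording and somewhat wider intervals. Power for the planned 4.5 points is 90.6% on 21 df or 89.5% on 15 df, the latter just under the planned 90% before any gain from covariates.
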